9.2.4 Response Criteria

9.2.4.1 Evaluation of Target Lesions

Immune related pathologic response criteria (irPRC)

irPRC response will be assessed as described by Stein et al by [name]/a board certified pathologist trained in irPRC assessment.⁵¹

Radiologic Response:

Complete Response (CR): Disappearance of all target lesions. Any pathological lymph nodes (whether target or non-target) must have reduction in short axis to <10 mm.

Partial Response (PR): At least a 30% decrease in the sum of the diameters of target lesions, taking as reference the baseline sum diameters.

Progressive Disease (PD): At least a 20% increase in the sum of the diameters of target lesions, taking as reference the smallest sum on study (this includes the baseline sum if that is the smallest on study). In addition to the relative increase of 20%, the sum must also demonstrate an absolute increase of at least 5 mm. (Note: the appearance of one or more new lesions is also considered progressions).

Stable Disease (SD): Neither sufficient shrinkage to qualify for PR nor sufficient increase to qualify for PD, taking as reference the smallest sum diameters while on study.

Special notes on the assessment of target lesions:

Lymph nodes: Lymph nodes identified as target lesions should always have the actual short axis measurement recorded and should be measured in the same anatomical plane as the baseline examination, even if the nodes regress to below 10mm on study. This means that when lymph nodes are included as target lesions, the 'sum' of lesions may not be zero even if complete response criteria are met, since a normal lymph node is defined as having a short axis of < 10 mm.

Target lesions that become 'too small to measure': All lesions (nodal and non-nodal) recorded at baseline should have their actual measurements recorded at each subsequent evaluation, even when very small (eg, 2mm). If the radiologist is able to provide an actual measure, that should be recorded, even if it is below 5mm. When such a lesion becomes difficult to assign an exact measurement, it is recommended to: If it is in the opinion of the radiologist that the lesion has likely disappeared, the measurement should be recorded as 0 mm. If the lesion is believed to be present and is faintly seen but too small to measure, a default value of 5 mm should be assigned (note: in case of a lymph node believed to be present and faintly seen but too small to measure, a default value of 5 mm should be assigned in this circumstance as well). This default value is derived from the 5 mm CT slice thickness (but should not be changed with varying CT slice thickness).

Lesions that split or coalesce on treatment: When non-nodal lesions ‘fragment’, the longest diameters of the fragmented portions should be added together to calculate the target lesion sum. Similarly, as lesions coalesce, a plane between them may be maintained that would aid in obtaining maximal diameter measurements of each individual lesion. If the lesions have coalesced such that they are no longer separable, the vector of the longest diameter in this instance should be the maximal longest diameter for the ‘coalesced lesion’.

9.2.4.2 Evaluation of Non-Target Lesions

Complete Response (CR): Disappearance of all non-target lesions and normalization of tumor marker level. All lymph nodes must be non-pathological in size (<10 mm short axis).

Note: If tumor markers are initially above the upper normal limit, they must normalize for a patient to be considered in complete clinical response.

Non-CR/Non-PD: Persistence of one or more non-target lesion(s) and/or maintenance of tumor marker level above the normal limits.

Progressive Disease (PD): Appearance of one or more new lesions and/or *unequivocal progression* of existing non-target lesions. Unequivocal progression should not normally trump target lesion status. It must be representative of overall disease status change, not a single lesion increase.

Although a clear progression of “non-target” lesions only is exceptional, the opinion of the treating physician should prevail in such circumstances, and the progression status should be confirmed at a later time by the review panel (or Principal Investigator). When the patient also has measurable disease: To achieve ‘unequivocal progression’ on the basis of the non-target disease, there must be an overall level of substantial worsening in non-target disease such that, even in presence of SD or PR in target disease, the overall tumor burden has increased sufficiently to merit discontinuation of therapy. A modest ‘increase’ in size of one or more non-target lesions is usually not sufficient to qualify for unequivocal progression status. When the patient has only non-measurable disease: To achieve ‘unequivocal progression’ on the basis of the non-target disease, there must be an overall level of substantial worsening such that the overall tumor burden has increased sufficiently to merit discontinuation of therapy. A modest ‘increase’ in the size of one or more non-target lesions is usually not sufficient to qualify for unequivocal progression status. Because worsening in non-target disease cannot be easily quantified (by definition: if all lesions are non-measurable) a useful test that can be applied when assessing patients for unequivocal progression is to consider if the increase in overall disease burden based on the change in non-measurable disease is comparable in magnitude to the increase that would be required to declare PD for measurable disease: i.e., an increase in tumor burden representing an additional 73% increase in ‘volume’ (which is equivalent to a 20% increase diameter in a measurable lesion). Examples include an increase in a pleural effusion from ‘trace’ to ‘large’, an increase in lymphangitic disease from localized to widespread, or may be described in protocols as ‘sufficient to require a change in therapy’. If

‘unequivocal progression’ is seen, the patient should be considered to have had overall PD at that point.

9.3 Progression-Free Survival

PFS is defined as the duration of time from start of nivolumab treatment to time of progression or death, whichever occurs first.

10. STATISTICAL CONSIDERATIONS

10.1 Study Design/Endpoints

10.1.1 Study Design

Patients will receive 1 dose of nivolumab, 480mg IV on Day -28 prior to planned surgery on or after Day 0 and up to/including Day +14. A 14 day window is allowable (as needed for scheduling purposes, or if clinically appropriate for patients with clinical benefit/improvement, if deemed safe by the treating physicians (surgeon & medical oncologist). Furthermore if clinically indicated patients may undergo surgery earlier (see Section 4.1.2 regarding early surgery, salvage treatment).

Patients will be observed for **perioperative grade 3-4 adverse events through day 100 (or day 30 post surgery – whichever is longer)** following the last dose of study drug(s). Safety and feasibility will be monitored continually throughout the study through biweekly meetings with investigators. A set of markers of immune reactivity measured in the tumor resection specimens, draining lymph nodes, and peripheral blood will be evaluated. Feasibility in this study means the successful completion of preoperative treatment and proceeding to surgery without any extended treatment related delays. Extended treatment-related delay is defined as > 28 days from preplanned Day 0 in this context (or accordingly >14 days from day +14).

10.1.2 Endpoints

Primary Endpoint

Safety and feasibility of neoadjuvant nivolumab administration in patients with newly diagnosed head and neck cancer and those with locoregional recurrence or oligometastatic disease undergoing surgical resection, measured by 1) frequency of drug-related adverse events occurring up to 100 days after the last dose of nivolumab or 30 days after surgery (whichever is longer), and 2) successful completion of preoperative treatment and proceeding to surgery without any extended treatment-related delays greater than 28 days from the preplanned day 0 (or 14 days from day +14).

Secondary Endpoints

Immune related pathologic response (irPRC)
As defined by Stein et al (CCR 2019)⁵¹

Major pathologic response rate

Defined as $\leq 10\%$ residual tumor in the resection specimen after neoadjuvant nivolumab

Progression-free survival

Progression-free survival will be measured from the time of initiation of nivolumab until radiologic or clinical progression or death.

Radiographic response rate

Response will be determined by RECIST version 1.1.

Laboratory correlates of immune activity and response

10.2 Sample Size, Analysis, and Accrual Rate

This study is investigating the safety and feasibility of neoadjuvant nivolumab administration in patients with locoregional newly diagnosed, recurrent or oligometastatic disease undergoing surgical resection. The study will enroll patients in two cohorts with an expected 12 patients in each cohort (although exact allocation may vary), who will undergo surgery in each cohort; the total sample size will be up to 26 patients. Subjects who sign a consent form but do not initiate protocol treatment for any reason (e.g., subjects who are screen failures), and patients who do not undergo surgical resection (for reasons unrelated to the study drug or toxicity) will be replaced and will not count towards our accrual goal.

The goal for the primary analysis of safety is to estimate the rate of DLTs (as defined in section 5.1) (AEs). We will provide the proportion of patients experiencing AEs, along with 95% confidence interval. Based on our study of neoadjuvant nivolumab in resectable lung cancer, we assume that at most 5% of patients will develop drug-related AEs of grade 3 or higher. The estimate and corresponding two-sided 95% confidence interval (CI) for each cohort is listed in the table below and may be updated if allocation between cohorts is not balanced:

| Observed number of patients with grade 3 or higher toxicity | Observed rate | 95% CI (Clopper-Pearson) |
|---|---------------|--------------------------|
| 0 | 0 | 0% - 26.5% |
| 1 | 8.3% | 0.2% - 38.5% |
| 2 | 16.7% | 2.1% - 48.4% |

For feasibility, the estimate of percent patient proceeding to surgery without any extended treatment related delays and the corresponding 95% CI based on 11-12 patients is, but may be updated if allocation between cohorts varies further:

| Observed number of patients proceeding to surgery without extended delay | Observed rate | 95% CI (Clopper-Pearson) |
|--|---------------|--------------------------|
| 12 | 100% | 73.5% - 100% |
| 11 | 91.7% | 61.5% - 99.8% |

However, cohort size (e.g. in the case of imbalanced enrollment) may be split 13/11, or 14/10, after consultation with the study statistician.

Surgical resection for head and neck cancers is standard of care. With regards to the recurrent population, this study targets a niche population, and historically there has been no dedicated trial for these patients. Typically surgeons perform at least 2-4 operations in patients appropriate for this study per month at a high volume academic institution, and thus expected accrual is 1-4 per month. For 26-patient study, it will take approximately 12-18 months with a high volume academic site such as Johns Hopkins University.

Endpoints:

Feasibility will be evaluated as the successful completion of preoperative treatment and proceeding to surgery without any extended treatment-related delays defined as >28 days from preplanned Day 0 in this context (or 14 days if surgery is performed Day +14).

Safety will be measured by:

- Frequency of drug-related adverse events occurring from the (first) dose of nivolumab up to 100 days after the last dose of study treatment or 30 days after surgery (whichever is longer).
- Frequency of serious adverse events occurring from the (first) dose of nivolumab up to 100 days after the last dose of study treatment or 30 days after surgery (whichever is longer).
- Frequency of clinical laboratory test by worst toxicity grade using NCI CTCAE v5 (as assessed at the time intervals outlined in the study calendar 4.10).

Safety and feasibility will be monitored continually throughout the study.

Safety stopping guideline: For the neoadjuvant nivolumab cohorts we will temporarily halt the accrual if the risk of grade 3-4 toxicities appears to be higher than 25% (i.e., posterior probability that the risk > 25% is 0.7 or higher). We use a stopping rule based on a Beta prior distribution with parameters 1 and 3. With this prior, there is 90% probability that this risk of high-grade toxicity is between 1.7% and 63.2%. The safety stopping rule for the two single-agent cohorts applies this prior distribution to the observed number of patients experiencing high-grade toxicity and to compute the resulting risk of such toxicities. If, given the data from patients already treated, the probability is at least 70% that the risk is greater than 25%, we will consider stopping treatment. Starting from the 2nd patients, the safety stopping guidelines are

shown in Table 1.

Table 1. Stopping rule for safety.

| Stop if there are this many grade 3 or higher AEs | 2 | 3 | 4 | 5 |
|---|-----|-----|------|----|
| In this many patients | 2-4 | 5-8 | 9-11 | 12 |

Operating characteristics of the safety stopping rule are shown below and are based on 5,000 simulations:

| Risk of AE | 0.15 | 0.20 | 0.25 | 0.30 | 0.35 | 0.40 |
|-----------------------|-------|------|-------|-------|------|-------|
| % of Time study stops | 16.7% | 30% | 42.2% | 55.4% | 69% | 78.7% |
| Expected sample size | 10.8 | 10 | 9.1 | 8.2 | 7.1 | 6.3 |

Feasibility stopping guideline: We will temporarily halt the accrual if the risk of delayed surgery due to neoadjuvant nivolumab appears to be higher than 25%. We use a stopping rule based on a Beta prior distribution with parameters 0.1 and 0.9. With this prior, there is 90% probability that this risk of high-grade toxicity is between 0 and 65%. If, given the data from patients already treated, the probability is at least 70% that the risk is greater than 25%, we will consider stopping accrual pending feasibility evaluation. Starting from the 2nd patients, the stopping rules are shown in Table 2.

Table 2. Stopping rule for feasibility.

| Number of patients whose surgery is delayed for >28 days | 2 | 3 | 4 | 5 |
|--|-----|-----|------|----|
| Out of this many patients | 2-4 | 5-8 | 9-11 | 12 |

Operating characteristics of the feasibility stopping rule are shown below and are based on 5,000 simulations:

| Risk of delayed surgery | 0.15 | 0.20 | 0.25 | 0.30 | 0.35 | 0.40 |
|-------------------------|-------|-------|-------|-------|-------|-------|
| % of Time study stops | 17.3% | 29.3% | 43.1% | 56.2% | 68.3% | 79.2% |
| Expected sample size | 10.8 | 10 | 9 | 8.1 | 7.1 | 6.2 |

We will report the proportion of patients experiencing high-grade toxicity with exact binomial 95% confidence intervals. The safety analysis population includes patients who receive one dose of nivolumab. We will also describe patient experiences with respect to feasibility as defined above. The analysis population for feasibility includes patients who receive one dose of nivolumab. All other adverse events will be similarly summarized by type and grade. Analyses of immune markers will be descriptive and/or graphical in nature.

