4.10 Study calendar

| Procedure | Screening (Days -42 to -29) ^a | Day -28 | Pre- surgical evaluation (Days -7 to -1)** | Day 0 Surgery (up to day +14) | Post- surgical evaluation (Days 21 to 42) | Follow-up visits (Every 3-4 months for 1 yr; then every 6 months for 2nd yr.) ^{\$\$} | At the time of recurrence | Survival Follow-up (every 12 months) |
|--|--|------------|--|---|---|---|---------------------------------|---|
| Clinical Assessments | | | | | | | | |
| Physical Exam | X | X | X | | X | X | X | |
| Vital Signs | X | X | X | | X | X | X | |
| Performance status (ECOG) | X | X | X | | X | X | X | |
| Concomitant medicines | X | X | X | | X | X | X | |
| Toxicity assessments | X | X | X | | X | X | X | |
| Electrocardiogram (EKG) | X | | | | | | | |
| Laboratory Tests | | | | | | | | |
| CBC with diff | X | X**** | X | | X | X | X | |
| Chemistry including LFT | X | X**** | X | | X | X | X | |
| # IF abnormal LFTs draw: Hepatitis B/C serology | (X) [#] | | | | | | | |
| TSH | X | | | | X | X | | |
| Free T4 and T3 | X | | | | | | X | |
| PT/INR and PTT | X | | X | | | | X | |
| Pregnancy Tests (WOCBP only) | X | | X | | X | | X | |
| Treatment | | | | | | | | |
| Nivolumab | | X | | | | | | |
| CT neck/chest with IV contrast* | X | | X | | | (X) | (X) | |
| MRI neck with IV contrast, optional† | (X) | | (X) | | | (X) | (X) | |

| Procedure | Screening (Days -42 to -29) | Day -28 | Pre- surgical evaluation (Days -7 to -1) | Day 0 (and up to day +14) Surgery | Post- surgical evaluation (Days 21 to 42) | Follow-up visits (Every 3- 4 months for 1 yr; then every 6 months for 2nd yr.) ^{§§} | At the time of recurrence | Survival Follow-up (every 12 months) |
|---|-----------------------------------|----------------|--|---|---|---|---------------------------------|---|
| Correlative Blood/Tissue/Stool Studies | | | | | | | | |
| PBMCs, Serum, plasma (Blood collection 100 cc's) | | X ^b | | X | X | X | X | |
| Tumor biopsy/sample | X | | | X (resection specimen) | | | X | |
| Stool Sample | | X ^c | X | | X | X | X | |
| Oral Rinse ^d | | X | | | X | X ^d | X | |
| Medical & Dietary Questionnaire | | X | | | X | X | X | |
| Survival | | | | | | | | X |

- a. screening labs are permitted to be used for treatment if completed within three (+3) days of day -28
- b. Research blood permitted to be collected anytime after consent and prior to Nivolumab infusion (Days -42 to day -28)

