6.2 Adverse Events

An Adverse Event (AE) is defined as any new untoward medical occurrence or worsening of a preexisting medical condition in a clinical investigation participant administered study drug and that does not necessarily have a causal relationship with this treatment. An AE can therefore be any unfavorable and unintended sign (such as an abnormal laboratory finding), symptom, or disease temporally associated with the use of investigational product, whether or not considered related to the investigational product.

The causal relationship to study drug is determined by a physician and should be used to assess all adverse events (AE). The causal relationship can be one of the following:

Related: There is a reasonable causal relationship between study drug administration and the AE.

Not related: There is not a reasonable causal relationship between study drug administration and the AE.

The term "reasonable causal relationship" means there is evidence to suggest a causal relationship.

Adverse events can be spontaneously reported or elicited during open-ended questioning, examination, or evaluation of a subject. (In order to prevent reporting bias, subjects should not be questioned regarding the specific occurrence of one or more AEs.)

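### The laboratory safety measure in section 10.2 has neither the time window of its two sibling measures nor a comparison with baseline, so it does not isolate nivolumab toxicity

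*Combined protocol and SAP*

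**What the plan says.** Section 10.2, under Endpoints, gives three ways in which safety will be measured.

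- The first is "Frequency of drug-related adverse events occurring from the (first) dose of nivolumab up to 100 days after the last dose of study treatment", extended to 30 days after surgery if that is later.
- The second, for serious adverse events, has the same window.
- The third is "Frequency of clinical laboratory test by worst toxicity grade using NCI CTCAE v5 (as assessed at the time intervals outlined in the study calendar" (section 4.10). It gives no start, end, baseline reference or attribution rule.

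The calendar marks CBC and chemistry at screening, Day -28, the pre-surgical evaluation (Days -7 to -1), the post-surgical evaluation (Days 21 to 42), the follow-up visits and recurrence. The follow-up column is headed "Follow-up visits (Every 3-4 months for 1 yr; then every 6 months for 2nd yr", and a footnote allows each visit to move by 28 days or as clinically indicated. TSH is marked at screening, post-surgery and follow-up. A further footnote says "screening labs are permitted to be used for treatment if completed within three (+3) days of day -28", so the first two draws may be a single sample.

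Three other places bear on the point. Sections 9.2.1 and 10.3 make patients evaluable for toxicity from their first treatment. Section 6 collects adverse events from first dose to 100 days after the last. The primary safety endpoint in section 10.1.2 is "frequency of drug-related adverse events occurring up to 100 days after the last dose of nivolumab or 30 days after surgery (whichever is longer"; it does not name the laboratory table.

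**The concern.** The window is written out for two measures and replaced by a pointer to the calendar for the third. Followed as written, that pointer takes in follow-up visits that can come after adjuvant radiotherapy or chemoradiotherapy (sections 4.1.1 and 4.6), and the recurrence visit. Abnormal values at those visits can have causes other than nivolumab.

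A worst grade is also not a change. Section 3.1.8 admits AST/ALT up to 3 times the upper limit of normal, platelets down to 100,000/mcL, neutrophils down to 1,000/mcL, and creatinine above normal if clearance is at least 40 mL/min. An entry abnormality that merely persists into the first post-dose sample can be tabulated as toxicity.

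Safety is the primary objective, and section 10.3 reports toxicities by cohort. With an expected 12 patients in a cohort, each patient placed in a grade category for a reason unrelated to the drug moves that category by 1/12 = 8.3 percentage points. Two analysts working from this sentence could produce different tables.

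**Working it through.** The plan states no figure for this measure, so there is none to reproduce. The neighbouring figures in section 10.2 were recomputed to see whether any depends on it. The Clopper-Pearson intervals for n = 12 (for example 0/12: 0 to 26.5%; 1/12: 0.2 to 38.5%), the Beta(1,3) 90% interval (1.7 to 63.2%) and the stopping boundaries (2 in 2-4, 3 in 5-8, 4 in 9-11, 5 in 12) all reproduce. None uses the laboratory measure.

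**1. Where the siblings' window ends.** The dose is on Day -28, so the 100-day limit is -28 + 100 = Day 72. For surgery on Day S, the 30-day limit is S + 30, which passes Day 72 only if S > 42. For planned surgery (Day 0 to Day +14) the window therefore ends on Day 72.

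**2. Scheduled CBC and chemistry draws.** Year 1 of follow-up has 12/4 = 3 to 12/3 = 4 visits, and year 2 has 12/6 = 2.

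| Draw | Number | After dose and by Day 72? |
|---|---|---|
| Screening | 1 | No, before dose |
| Day -28 | 1 | No, before dose |
| Pre-surgical, Days -7 to -1 | 1 | Yes |
| Post-surgical, Days 21 to 42 | 1 | Yes |
| Follow-up, years 1 and 2 | 5 to 6 | First visit only, if early |
| Total | 9 to 10, plus recurrence | 2, possibly 3 |

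If screening also serves as the Day -28 sample, the total is 8 to 9. If the post-surgical days are counted from a Day +14 operation, the latest is 14 + 42 = Day 56, still inside.

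The calendar does not say what the follow-up visits are timed from. Timed from surgery on Day 0, a 3-month visit falls near Day 91; moved forward 28 days it falls on Day 63, which would be the third in-window draw. A 4-month visit (about Day 122) moved the same way falls on Day 94, outside.

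**3. Size under each reading.** If sections 9.2.1 and 10.3 are taken to exclude pre-dose samples, the literal reading still pools 2 + 5 to 6 = 7 to 8 scheduled draws, of which 2 or 3 are in the window. If not, it pools 9 to 10. For TSH, scheduled post-dose draws are 1 + 5 to 6 = 6 to 7, of which 1, possibly 2, are in the window.

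**4. Illustration.** The documents give no background rate of high-grade laboratory values. Let q be an assumed chance, per draw, of a grade 3 or higher value not caused by nivolumab, and assume draws are independent. The chance of at least one in k draws is 1 - (1 - q)^k.

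| q | k = 2 | k = 7 to 8 | k = 9 to 10 |
|---|---|---|---|
| 1% | 2.0% | 6.8 to 7.7% | 8.6 to 9.6% |
| 2% | 4.0% | 13.2 to 14.9% | 16.6 to 18.3% |
| 5% | 9.8% | 30.2 to 33.7% | 37.0 to 40.1% |

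This shows how a worst-grade summary grows with the number of draws. It is not an estimate of the bias: q would differ between draws, and draws within a patient are correlated.

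**The case against.** The best reply is that the reference to the calendar may only say when samples are taken, with the analysis window left to the rest of the plan. Sections 9.2.1 and 10.3 start toxicity evaluation at first treatment; section 6 ends adverse event collection at 100 days; section 10.1.1 observes grade 3-4 events over the siblings' window; and section 5.1 limits dose-limiting toxicities, including the hepatic laboratory criteria, to drug-related events in that same window.

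Much of this stands. A reader might infer that screening values are certainly pooled with toxicity. The documents do not say so, and the two start rules point the other way, so that part is an ambiguity. The end date is different: none of these sections expressly closes the laboratory table, and the one sentence that defines it points to section 4.10. No section supplies a baseline comparison.

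Four stronger readings are tempting and not supported.

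- **That the measure says nothing about nivolumab.** It contains the pre-surgical and post-surgical draws, so it is non-specific rather than uninformative.
- **That it contradicts section 6.2**, where an adverse event is "any new untoward medical occurrence or worsening of a preexisting medical condition". That section defines an adverse event; the laboratory table is listed as a separate summary.
- **That it biases the comparison against Cohort 2.** Cohort 2 may have had earlier chemoradiation, but both cohorts meet the same organ-function limits and both may receive adjuvant therapy. Section 2.1 calls further postoperative radiotherapy challenging after recurrence, so contamination from adjuvant therapy could be greater in Cohort 1. The net direction is not established.
- **That the primary result or the stopping rules are compromised.** They rest on adverse events, dose-limiting toxicities and delay of surgery.

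**Conclusion.** The point holds for a supporting, descriptive safety table. As worded, it has no end date and no baseline rule, and on the literal reading most of the scheduled draws feeding it lie outside the period used for the other two safety measures: only 2, possibly 3, of about 9 to 10 lie inside, or of 7 to 8 if pre-dose samples are excluded. The table would therefore not isolate nivolumab toxicity. No sample size, interval or boundary changes.

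The count assumes the nominal calendar, dosing on Day -28, surgery by Day +14 and follow-up timed from about surgery. How often an entry abnormality would score depends on the CTCAE version 5.0 tables, which the documents do not reproduce; any test that the scale itself grades against the patient's own baseline would escape that part.

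**What to change.** Reword the third measure in section 10.2 along these lines: for each laboratory test, the frequency of the worst CTCAE v5 grade after the first dose that is worse than the grade of the last value before infusion, among samples taken up to 100 days after nivolumab or 30 days after surgery, whichever is later. Summarise later values, including those at recurrence, in a separate table. A shift table from baseline to worst grade, by cohort, would be a convenient display but is optional.

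The cost is one sentence and one further table, from data already scheduled for collection. There are two limits. Changes caused by surgery stay in the window, because the post-surgical draw falls inside it and the rewording adds no attribution rule. Late values move out of the main table; since TSH has only one scheduled draw certain to fall in the window, the second table should be reported routinely so that no late signal is lost.
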